3. PARTICIPANT SELECTION

3.1 Eligibility Criteria

Participants must meet the following criteria on screening examination to be eligible to participate in the study:

Subjects with CLL/SLL:

3.1.1 Subjects must be diagnosed with CLL / SLL (chronic lymphocytic leukemia / small lymphocytic lymphoma) based on the standard histologic and immunophenotypic criteria described in the WHO classification of lymphoid malignancies, including immunophenotypic confirmation that the tumor cells co-express B cell antigens CD19 / 20 and CD5. Mantle cell lymphoma should be excluded based on positive staining of the tumor cells for CD23, or the absence of staining of the tumor cells for cyclin D1 or the absence of t(11;14). This diagnosis should be confirmed at a Dana-Farber Harvard Cancer Center institution (DFCI, BWH, MGH, BIDMC) within approximately one month after the subject is registered. Any question on histology confirmation should be brought to the attention of the Principal Investigator.

3.1.2 Participants must have measurable disease, defined as lymphocytosis \geq 5,000 / ul, or at least one palpable or CT measurable lesion $>$ approximately 1.5 cm, or bone marrow involvement $>$ approximately 30%.

3.1.3 Subjects must have relapsed after at least one prior purine analogue-containing regimen (fludarabine, cladribine or pentostatin), OR at least two non-purine analogue containing regimens.

Subjects with T-LGL:

T-LGL judged by the investigator to require therapy based upon:

- 1) Severe neutropenia (absolute neutrophil count $<$ 500/microL)
- 2) Moderate neutropenia (absolute neutrophil count $<$ 1000/microL) with recurrent infections
- 3) Symptomatic or transfusion dependent anemia
- 4) Severe thrombocytopenia ($<$ 50,000/microL)
- 5) Hepatic infiltration resulting in abnormal liver function tests
- 6) Symptomatic splenomegaly

Patients with previously untreated or relapsed/refractory disease will be eligible

All Subjects:

3.1.4 Age \geq 18 years.

3.1.5 Life expectancy of greater than 3 months.

3.1.6 ECOG performance status \leq 2 (Karnofsky \geq 60%, see Appendix B).

3.1.7 Participants must have normal organ function as defined below:

- total bilirubin $\leq 1.5X$ institutional ULN unless due to indirect hyperbilirubinemia related to Gilbert's syndrome or hemolysis, or to disease infiltration
- AST (SGOT)/ALT (SGPT) $\leq 5 X$ institutional upper limit of normal
- creatinine $\leq 2X$ institutional ULN

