10. MEASUREMENT OF EFFECT

Responses will be formally assessed initially at the conclusion of the 1st 28 day cycle, then at the conclusion of three cycles (three months), and then every three months thereafter, until disease progression, start of another treatment, or death. Response will be assessed in two ways: (1) By NCI-WG 1996 criteria³ (as updated in the IWCLL 2008 criteria Section 10.2)¹⁹ without the use of CT scans. In this case lymph nodes will be assessed based on physical exam measurements; (2) With the incorporation of CT findings as suggested for clinical trials in IWCLL 2008. Thus CT scans will be performed on all patients at the end of the 1st month, 3rd month and 6th month, if still on study we will evaluate the impact of the CT scans (1) if used only to confirm CR; (2) if used to assess lymphadenopathy regardless of PE findings. After the 6 month evaluation, further CT scans will generally not be done, but may be done at the discretion of the treating physician.

Following the initial screening bone marrow biopsy, additional bone marrow biopsies will be performed only to confirm complete remission.

T-LGL Response Criteria²¹:

Response to treatment should be evaluated by history, physical examination, and complete blood count with differential:

- Complete response — A hematologic complete response is defined as the complete normalization of blood counts (ie, hemoglobin >12 g/dL; platelets >150,000/microL; absolute neutrophil count >1500/microL; absolute lymphocyte count <4000/microL) in the setting of a circulating LGL count of less than 500/microL.
- Partial response — A hematologic partial response is defined as an improvement in blood counts that does not meet criteria for complete remission (eg, an absolute neutrophil count >500/microL or decreasing transfusion requirements).
- Treatment failure — Treatment failure is defined as an inability to achieve an at least partial response after four months of therapy.
- Progressive disease — Progressive disease is defined as a worsening of cytopenias, hepatomegaly, or splenomegaly

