14.2.2 Phase II

The Phase II portion is a single arm study which consists of determining the overall response rate of pyrimethamine in relapsed CLL/SLL and T-LGL patients. The overall response rate is not expected to differ between these two diseases and therefore one overall response rate will be reported. A 35% overall response rate will be considered promising. The first response evaluation will be assessed after the first cycle of treatment then at the end of three cycles.

Six Phase I patients treated at the MTD of pyrimethamine will be enrolled in the Phase II part of the study. A Simon's two stage optimal design is used to compute the sample size. A total number of 26 patients is needed in order to detect a 35% response rate, assuming the ORR for the null hypothesis is 10%, with 90% power and 10% type I error. The study will stop early if only 1 or 0 responses out of the first 10 patients is observed, and the drug will not be declared promising if less than 5 responses are seen in the total 26 patients. The probability of stopping at the first stage if the true ORR is less than 35% is 0.736.

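### T-LGL patients may enter for liver or spleen disease alone, but response is scored on blood counts only, so the primary ORR can misclassify them in either direction

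*Combined protocol and SAP*

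**What the plan says.** Section 3.1 lists six T-LGL indications for therapy. Four are cytopenias. The other two are "Hepatic infiltration resulting in abnormal liver function tests" and "Symptomatic splenomegaly". The list works as alternatives, since severe neutropenia and moderate neutropenia with infections are separate items, so neither organ indication needs a low count.

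Section 10 names the assessments: "Response to treatment should be evaluated by history, physical examination, and complete blood count with differential". The categories are then defined as follows.

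- CR: "A hematologic complete response is defined as the complete normalization of blood counts", with fixed limits (hemoglobin >12 g/dL, platelets >150,000, ANC >1500 and ALC <4000/microL) and circulating LGL below 500/microL.
- PR: "A hematologic partial response is defined as an improvement in blood counts that does not meet criteria for complete remission", with the examples "an absolute neutrophil count >500/microL or decreasing transfusion requirements".
- Progression: "Progressive disease is defined as a worsening of cytopenias, hepatomegaly, or splenomegaly".

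Section 14.6.2 puts every eligible participant in the main response analysis. Section 14.2.2 pools CLL/SLL with T-LGL, so that "one overall response rate will be reported". The Section 9 calendar does not require radiology for T-LGL.

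**The concern.** Organ disease can bring a T-LGL patient into the trial and can count against the drug as progression, but its improvement never counts as response. A spleen that returns to normal, or liver tests that recover, earn nothing by themselves. In the other direction, a patient whose counts were never abnormal may be scored a responder while the organ disease is unchanged.

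These patients enter the Phase II primary endpoint directly. They count in the first-stage rule (stop at 0 or 1 response in 10) and in the final rule (at least 5 of 26 needed). With thresholds this small, one or two misclassified patients matter.

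**Working it through.** **Comparing the definitions.** Take a hypothetical patient entered for symptomatic splenomegaly with hemoglobin 13 g/dL, platelets 180,000, ANC 2,500 and ALC below 4000.

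- LGL at or above 500 throughout: CR is blocked by the LGL limit, and no cytopenia is left to improve. There is no clear route to response even if the spleen normalises.
- LGL at or above 500 at entry, then below 500: CR is met, whatever happens to the spleen.
- LGL below 500 at entry: every printed CR limit is met before dosing.
- One count slightly low at entry: any small rise can be called PR, because no minimum is given. The ANC example (>500) is a level that a patient without severe neutropenia already exceeds.

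The liver and spleen rows of the Section 10.2 table do not fill the gap. That table is written for CLL (marrow B-lymphoid nodules, changes attributed to CLL). Section 3.1.8 asks all subjects for an IWCLL indication, but Appendix A itself includes symptomatic splenomegaly, so it does not bring in a cytopenia requirement.

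**Reproducing the design (Section 14.2.2).** Inputs: n1 = 10, stop if X1 ≤ 1; N = 26, promising if the total is ≥ 5; null 10%, target 35%.

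P(promising) = Σ over x ≥ 2 of P(X1 = x) × P(X2 ≥ 5 − x), with X1 ~ Bin(10, p) and X2 ~ Bin(16, p).

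- Stop at p = 0.10: 0.3487 + 0.3874 = 0.736, the plan's figure.
- Type I error: 0.1937×0.2108 + 0.0574×0.4853 + 0.0112×0.8147 + 0.0016 = 0.079, within the 10% limit.
- Power at p = 0.35: 0.1757×0.9549 + 0.2522×0.9902 + 0.2377×0.9990 + 0.2485 = 0.903, matching 90%.

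**Adding misclassified patients.** The documents give neither the number of T-LGL patients nor the number entering on organ disease alone, so the counts below are assumptions. The affected patients are placed at random across the two stages (hypergeometric weights), and all others respond at p.

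One structural failure, p = 0.35: power is 0.8663 if it falls in stage 1 and 0.8993 if in stage 2, so (10/26)×0.8663 + (16/26)×0.8993 = 0.887.

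One automatic responder, p = 0.10: (10/26)×0.2099 + (16/26)×0.1457 = 0.170.

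| Structural failures | Automatic responders | False positive at 10% | Power at 35% |
|---|---|---|---|
| 0 | 0 | 0.079 | 0.903 |
| 1 | 0 | 0.069 | 0.887 |
| 2 | 0 | 0.060 | 0.867 |
| 4 | 0 | 0.043 | 0.818 |
| 0 | 1 | 0.170 | 0.935 |
| 0 | 2 | 0.321 | 0.957 |
| 2 | 1 | 0.138 | 0.909 |
| 4 | 2 | 0.232 | 0.915 |

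With failures only, the first-stage stopping probability at 35% rises from 0.086 to 0.115 (2 of 26) or 0.151 (4 of 26).

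**The case against.** The strongest reply is that hematologic criteria from a cited T-LGL source are a legitimate choice, and that the affected group may be small or empty. Section 2.2 calls T-LGL uncommon and describes patients with anemia, neutropenia, infection or fatigue, not organ-only disease. That stands as a limit on size: with no such patient there is no effect. It does not remove the mismatch, because Section 3.1 explicitly admits these patients.

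A reader might go further and infer that organ-entry patients cannot respond and are built-in failures that erode power. The documents do not support that. PR is open to any improvement in a count that is not yet normal. CR is reachable if LGL falls below 500 with ALC below 4000. ALC and LGL are themselves counts, so a fall in either could be argued to be an improvement. Some of these patients meet CR at entry. With 2 failures and 1 automatic responder, power is 0.909, no lower than the design's 0.903.

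A reader might also infer that CLL patients get response credit for spleen shrinkage alone. They do not: PR in Section 10.2 needs two group A criteria plus one group B criterion. Copying only the spleen row into the T-LGL rules would create a looser standard within the same pooled rate.

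**Conclusion.** The eligibility list and the response definitions do not match. For T-LGL patients entered only for liver or spleen disease, the primary endpoint does not measure the condition that made them eligible, and applying Section 10 as written can misclassify them either way. The direction cannot be predicted from the documents.

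The larger numerical risk is a false positive: one automatic responder among 26 takes the error rate at a 10% ORR to 0.170, above the stated 10%. One structural failure costs about 1.7 points of power (0.903 to 0.887). These figures rest on assumed numbers of affected patients, random placement across stages, and unchanged response rates in everyone else. The mismatch itself rests on the text alone. It should be corrected, but it does not show that the design is underpowered.

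**What to change.** Amend Section 10 before any response counting towards Phase II is scored, including those of the six Phase I patients carried over.

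1. State that a T-LGL patient whose baseline counts already meet the hematologic CR limits cannot be scored as a hematologic CR on those counts.
2. Require for PR a stated minimum improvement from baseline in a count that was abnormal at entry.
3. Reconcile Section 3.1 with Section 10, so that patients entered only under indication 5 or 6 have a prespecified response definition tied to the qualifying organ finding. The physical examination and liver tests already on the calendar can supply the data. State how spleen size is measured: radiology is not required for T-LGL, and the calendar's note on examination measurements covers palpable nodes only.
4. Report the ORR with and without these patients as a sensitivity analysis.

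The cost is amendment text, slightly more adjudication and one extra tabulation, with no new visits or tests. The main weakness is that spleen size judged by examination is imprecise.

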10.1 Progression-Free Survival

Progression-Free Survival (PFS) is defined as the duration of time from start of treatment to time of objective disease progression or death, whichever occurs earlier.

10.2 Antitumor Effect – Hematologic Tumors

Parameter	CR*	PR*	PD*
Group A			
Lymphadenopathy [^]	None > 1.5 cm	Decrease ≥50%	Increase ≥50%
Hepatomegaly	None	Decrease ≥50%	Increase ≥50%
Splenomegaly	None	Decrease ≥50%	Increase ≥50%
Blood lymphocytes	<4000/μL	Decrease ≥50% from baseline	Increase ≥50% over baseline
Marrow [#]	Normocellular, < 30% lymphocytes, no B-lymphoid nodules.	≥ 30% lymphocytes, or B-lymphoid nodules, or not done	Increase of lymphocytes to more than 30% from

			normal.
	Hypocellular marrow defines CRi		
Constitutional Symptoms@	None	Any	Any
Group B			
Platelet count	> 100 000/ μ L	> 100 000/ μ L or increase \geq 50% over baseline	Decrease of \geq 50% from baseline secondary to CLL
Hemoglobin	> 11.0 g/dL (untransfused and w/o erythropoietin)	> 11 g/dL or increase \geq 50% over baseline	Decrease of > 2 g/dL from baseline secondary to CLL
Neutrophils#	> 1500/ μ L	> 1500/ μ L or > 50% improvement over baseline	Any

* CR (complete remission): all of the criteria have to be met, and patients have to lack disease-related constitutional symptoms

* PR (partial remission): at least two of the criteria of group A plus one of the criteria of group B have to be met. PR to be held at least two months and confirmed by restaging.

* SD is absence of progressive disease (PD) and failure to achieve at least a PR; PD: at least one of the above criteria of group A or group B has to be met.

^Sum of the products of multiple lymph nodes (as evaluated by CT scans in clinical trials, or by physical examination in general practice).

#These parameters are irrelevant for some response categories.

@Constitutional symptoms: Unintentional weight loss \geq 10% within the previous 6 months, significant fatigue (ECOG PS 2 or worse, Fevers >100.5F or 38.0 C for 2 or more weeks without other evidence of infection, night sweats >1 month without evidence of infection

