5.5 Duration of Therapy

Initial response assessment will occur after 28 days of study therapy. Those subjects with stable or responding disease may continue on study indefinitely if their treating physician and the Principal Investigator feel that they are deriving clinical benefit. Subjects with significant adverse events or progressive disease should be removed from study.

Duration of therapy will depend on individual response, evidence of disease progression and tolerance. In the absence of significant adverse events, treatment may continue indefinitely or until one of the following criteria applies:

- Disease progression,
- Intercurrent illness that prevents further administration of treatment,
- Unacceptable adverse event(s),
- Participant decides to withdraw from the study, or

- General or specific changes in the participant's condition or compliance render the participant unacceptable for further treatment in the opinion of the treating investigator.

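### The CLL/SLL lymphocyte criterion for progression has no absolute floor, so a patient with a normal count can be scored PD on a rise that still meets the table's own CR limit

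*Combined protocol and SAP*

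**What the plan says.** The table in Section 10.2 gives the blood-lymphocyte row three cells. CR is an absolute limit, a count below 4,000/µL. PR is "Decrease ≥50% from baseline". PD is "Increase ≥50% over baseline". The combination rule for progression is "PD: at least one of the above criteria of group A or group B has to be met".

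Other PD cells carry conditions that the lymphocyte cell lacks. Platelet and hemoglobin falls count only if due to CLL, and the marrow cell names an absolute level of 30% lymphocytes. The footnote "These parameters are irrelevant for some response categories" is attached to the marrow and neutrophil rows, not to lymphocytes. The table asks for confirmation of a PR but not of a PD.

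Criterion 3.1.2 defines measurable disease by alternatives: lymphocytosis of at least 5,000/µL, "or at least one palpable or CT measurable lesion" over about 1.5 cm, or marrow involvement above about 30%.

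Three sections act on a PD. Section 5.5 states: "Subjects with significant adverse events or progressive disease should be removed from study". Section 10.1 makes objective progression a PFS event. Section 14.6.2 counts progressive disease as treatment failure in the response analysis.

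Section 10 says that CLL/SLL response follows NCI-WG 1996 as updated by IWCLL 2008, and points to Section 10.2.

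**The concern.** SLL is a target disease, and a patient may enter on a node or marrow with a normal lymphocyte count. At that level a 50% rise can be ordinary variation or a minor infection. A relative threshold without a floor treats it like a 50% rise in established lymphocytosis.

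The outcome is costly because the criterion acts alone. The first formal assessment is at the end of cycle 1, while a PR must be held for two months. A PD at month 1 therefore always precedes any confirmed PR. The Phase II rule in Section 14.2.2 turns on single patients: 1 versus 2 responses in the first 10, and 4 versus 5 in 26.

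**Working it through.** The plan states no figure on this point, so there is none to reproduce. The check has two parts.

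**1. Threshold arithmetic (document figures only).** The PD line is 1.5 × baseline.

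| Baseline (/µL) | PD line (/µL) | Below CR limit of 4,000? | Below lymphocytosis of 5,000? |
|---|---|---|---|
| 1,200 | 1,800 | yes | yes |
| 2,000 | 3,000 | yes | yes |
| 2,666 | 3,999 | yes | yes |
| 3,333 | 4,999.5 | no | yes |
| 5,000 | 7,500 | no | no |

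- The CR and PD cells overlap when 1.5 × baseline < 4,000, that is for baselines up to about 4,000 / 1.5 = 2,666/µL.
- The PD line falls short of the protocol's lymphocytosis threshold when baseline < 5,000 / 1.5 ≈ 3,333/µL.

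**2. Chance of crossing by noise (illustration).** Assumptions, none from the documents: log-normal counts, no true change, and the same within-person CV at baseline and follow-up.

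- σ = √ln(1 + CV²). The log ratio of two counts has standard deviation σ√2.
- Per assessment, P = 1 − Φ(ln 1.5 / (σ√2)), with ln 1.5 = 0.4055.
- At CV 20%: σ = 0.198, σ√2 = 0.280, z = 0.4055 / 0.280 = 1.448, P = 7.4%.
- For any of three assessments (months 1, 3 and 6) all three share one baseline, so they are not independent. With u the standardized baseline error, P = 1 − E[Φ(ln 1.5/σ + u)³].

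| Assumed CV | One assessment | Any of three |
|---|---|---|
| 15% | 2.7% | 6.8% |
| 20% | 7.4% | 16.8% |
| 25% | 12.2% | 25.9% |
| 30% | 16.4% | 33% |

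These chances apply only to patients with normal counts. The documents give neither that share nor the within-person variability, so the figures cannot be turned into an effect on the trial's ORR or PFS.

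**The case against.** **The table summarizes outside criteria.** Section 10 cites NCI-WG 1996 and IWCLL 2008, and a floor may exist there. This cannot be checked from the documents. It limits the finding to the printed rule, but the protocol restates no floor and assessors will work from the table.

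**The table cannot be read cell by cell.** Constitutional symptoms show any value for both PR and PD, and neutrophils show any value for PD. Read literally with the one-criterion rule, every patient would progress at every visit. This is fair, and it shows that the table needs judgment. But those cells plainly do not discriminate between categories, whereas the lymphocyte cell is a specific numeric threshold that an assessor would apply as written.

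**A later PD need not undo a response.** A count-based PD at month 6 does not erase a PR already confirmed. This stands: ORR failure follows only where the PD comes first.

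**A stronger reading on the PR side.** A reader might infer that the matching fall of 50% produces false PRs in the same way. The documents do not support that. PR needs "at least two of the criteria of group A plus one of the criteria of group B have to be met", held for two months and confirmed. Under the same noise model a fall of at least 50% at two consecutive assessments has a chance of only about 0.004% (CV 15%) to 1.8% (CV 30%). A sustained drug leukopenia could last longer, since leukopenia is listed in Section 6.1.1, but nothing in the documents sizes it. The PR marrow cell also already gives credit for "≥ 30% lymphocytes, or B-lymphoid nodules, or not done", so the lymphocyte credit may change little. Voiding the row for PR while keeping two Group A criteria could leave a node-only patient without organomegaly unable to reach PR.

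**Conclusion.** The point holds for the progression cell. As printed, a lone rise of 50% within the normal range is PD for patients whom 3.1.2 admits. For baselines up to about 2,666/µL the same count can also satisfy the CR lymphocyte cell. That contradiction follows from the protocol's own figures and needs no assumption.

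The frequency does rest on assumption: 3-16% per assessment and 7-33% over three, for patients with normal counts and a within-person CV of 15-30%. A reader might infer that the primary ORR is biased by a similar amount. The documents do not support that, because the share of such patients is unknown and T-LGL patients in the pooled Phase II have separate criteria. The correction is worth making before Phase II responses are scored.

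**What to change.** Reconcile the lymphocyte PD cell in Section 10.2 with the CR cell, with criterion 3.1.2 and with the criteria cited in Section 10. For scoring ORR and PFS, let a rise of at least 50% over baseline count as PD only when the count also reaches 5,000/µL, the lymphocytosis threshold already in 3.1.2. Leave the nodal, organ, marrow and cytopenia criteria for PD, and the PR cell, unchanged.

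The CR and PD lymphocyte cells can then no longer both be met, since 5,000 exceeds 4,000. Only baselines below about 3,333/µL are affected. From 1,200/µL the rise would have to be 5,000 / 1,200 = 4.17-fold.

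The cost is one phrase in the table, with no new data or visits. The downside is that a true rise staying below the threshold, such as 1,200 to 4,900/µL, is not PD on this row alone and must be picked up by another criterion. Section 5.5 ties removal from study to progressive disease, so the sponsor must also reconcile how the scoring definition relates to stopping treatment. No rule for that is proposed here.

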- be demonstrated. At a minimum, hyperuricemia, hydration, and electrolyte disturbances should be monitored closely and addressed promptly.
- 2 CT scans (chest/abdomen/pelvis) to be performed at screening in all patients and again at the end of the 1st, 3rd and 6th months of therapy; subsequent scans shall be at the discretion of the treating physician if needed for adequate response evaluation.
 - 3 Please see Section 8.3 "Determination of CLL Biologic Prognostic Factors" for details on sample collection.
 - 4 Diary dispensed with study drug and retrieved at scheduled visits.
 - 5a One heparin-anticoagulated green top tube (pharmacokinetic studies) to be collected during screening, on cycle 1 day 1 prior to drug; prior to drug on one day among days 2, 3, 4 or 5, (optional); and prior to dose (trough) at each subsequent clinic visit as per Section 8.1, above. A heparin-anticoagulated green top tube will also be collected at time of off study visit and once again 2-4 weeks later if the patient has not started additional therapy. All samples are to be delivered to the [name] lab on Mayer 5. This includes BIDMC patients.
 - 5b Two 6 cc heparinized blood for cell isolation (pharmacodynamic studies) is to be collected during screening, on cycle 1 day 1 prior to drug and approximately two hours after drug administration, prior to dose (trough) on days 2, 3 4 or 5 of therapy, pre drug on cycle 1 days 8, 15, and 22, cycle 2 days 1 and 15, and day 1 of subsequent cycles monthly up to cycle 6. Pharmacodynamic studies will also be collected at time of off study visit, 2-4 weeks later if the patient has not started additional therapy, and lastly at the 3 month follow up appointment (if subsequent therapy has not started). These are to be delivered to the [name] lab on Mayer 5. This includes BIDMC patients.
 - 6 These laboratory tests will be done at baseline, at the end of cycles 1, 3, 6, end of treatment, and every 3-6 months in follow-up.
 - 7 Bone marrow biopsy will be done at screening (unless done within previous 6 months and the Principal Investigator feels it does not need to be repeated, or if prior marrow was positive and the patient has not had CLL treatment since) and thereafter only to confirm CR. Confirmation of complete response by bone marrow biopsy should occur approximately 3 months after the clinical criteria for CR are first met. Bone marrow biopsy is not required at off study.

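### CLL/SLL response table (10.2): cells that are always satisfied sit inside a rule that counts criteria, so PR and PD cannot be assigned as printed

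*Combined protocol and SAP*

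**What the plan says.** Section 10.2 classifies CLL/SLL response from a table of group A and group B rows.

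- **PR:** "at least two of the criteria of group A plus one of the criteria of group B have to be met".
- **PD:** "PD: at least one of the above criteria of group A or group B has to be met".
- **SD:** neither PD nor PR.
- **CR:** every criterion met, with no minimum number of involved sites.

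Three rows matter here:

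- Marrow (group A), PR cell: "≥ 30% lymphocytes, or B-lymphoid nodules, or not done".
- Constitutional symptoms (group A), in the order CR, PR, PD: "Constitutional Symptoms@ None Any Any".
- Neutrophils (group B), end of the PR cell followed by the PD cell: "50% improvement over baseline Any".

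A footnote marked # says that its rows do not bear on certain response categories, but does not name those categories. It is attached to marrow and neutrophils. Constitutional symptoms carry a different mark, @, which only defines the symptoms.

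Study Calendar footnote 7 has a marrow biopsy at screening and "thereafter only to confirm CR". Section 3.1.2 accepts lymphocytosis, "or at least one palpable or CT measurable lesion", or marrow involvement as measurable disease. Section 14.6.2 turns an otherwise complete response without a restaging marrow into a PR.

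**The concern.** A rule that counts criteria works only if each counted cell can be failed. Here several cannot. Because marrow is repeated only to confirm CR, 'not done' is the usual state, and 'Any' is satisfied by definition. The result then depends on which cells an assessor chooses to count, and 10.2 does not say. Nor does it say which category prevails when a patient meets both PR and PD.

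For CLL/SLL patients this table supplies the response that enters the Phase II primary endpoint (ORR, 14.2.2) and the progression event for PFS (10.1). T-LGL patients have their own criteria in section 10 and are not affected.

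**Working it through.** **1. The plan's own design.** Inputs from 14.2.2: null ORR 10%, target 35%, stop if at most 1 of the first 10 respond, promising if at least 5 of 26 respond.

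- P(stop at stage 1) = (1−p)^10 + 10p(1−p)^9. At p = 0.10 this is 0.349 + 0.387 = 0.736, the plan's figure. At p = 0.35 it is 0.086.
- P(promising) = Σ from x = 2 to 10 of C(10,x) p^x (1−p)^(10−x) × P(Bin(16,p) ≥ max(0, 5−x)). At p = 0.10 this is 0.079, and at p = 0.35 it is 0.903. Both fit the stated 10% type I error and 90% power.

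**2. The table under three readings.** 'Adequate' means platelets > 100,000/µL, hemoglobin > 11 g/dL or neutrophils > 1500/µL. No repeat marrow is assumed.

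| Test patient | Every cell counts | # rows dropped | No uninformative cell counts |
|---|---|---|---|
| Unchanged, at least one adequate count | PR and PD | PD | neither (SD) |
| Unchanged, all three counts low | PD | PD | neither (SD) |
| Lymphocytosis only, 90% fall, adequate counts | PR and PD | PR and PD | neither (SD unless CR is met) |
| Two sites, each down 60%, adequate counts | PR and PD | PR and PD | PR |

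- *Every cell counts.* Marrow 'not done' and symptoms 'Any' give two group A criteria, and an unchanged adequate count gives the group B criterion. The two-month confirmation does not help, because an unchanged state also persists. PD is met by everyone.
- *# rows dropped.* Symptoms 'Any' still supplies one group A criterion, so one real change, with adequate platelets or hemoglobin, gives PR. Symptoms 'Any' also still gives PD to everyone.
- *No uninformative cell counts.* PD behaves sensibly, but a patient with one abnormal group A parameter can collect at most one group A criterion. The routes left are CR, or 14.6.2 when CR is met apart from an unassessed marrow.

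**3. Size if responders are lost.** Let q be the share of would-be responders who cannot reach PR and do not reach CR. The documents give no such share, so q is assumed. The effective rate is 0.35 × (1−q).

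| q | Effective ORR | Power of 1/10, 4/26 |
|---|---|---|
| 0 | 0.350 | 0.903 |
| 10% | 0.315 | 0.850 |
| 20% | 0.280 | 0.772 |
| 30% | 0.245 | 0.666 |

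**4. Size if non-responders are counted.** Let s be the share of non-responders recorded as PR, also assumed. With a true ORR of 10% the effective rate is 0.10 + 0.90s. For s = 0, 10% and 20% this is 0.10, 0.19 and 0.28, and the chance of declaring the drug promising is 0.079, 0.44 and 0.77.

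**The case against.** The strongest reply is that no sensible assessor would count an 'Any' cell. The documents support this. Section 14.6.2 lists stable disease as a category, section 5.5 provides for patients with stable disease, and 10.1 asks for objective progression. All three would be pointless if 'Any' counted toward PD. The CR footnote also names constitutional symptoms as a condition beside the criteria. Section 10 refers to NCI-WG 1996 as updated by IWCLL 2008, and those sources, not available here, may settle which rows count.

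Much of this stands. It rules out two inferences a reader might draw: that ORR and the PD rate would both come out near 100% in CLL/SLL, and that the Simon cut-offs are meaningless. The first takes the extreme reading as the intended one. Even on that reading, no-change PR needs an adequate blood count and needs marrow to count.

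A reader might also infer that single-site patients can never respond. They can: CR has no minimum number of sites, and 14.6.2 offers a route to PR.

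What the reply does not answer is that the protocol prints its own counting rule. The # footnote names no categories and leaves out constitutional symptoms. Once the uninformative cells are set aside, nothing says how a patient with one abnormal group A parameter reaches PR.

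**Conclusion.** The point holds for CLL/SLL. The printed PR and PD rules cannot be applied as written, and each way of repairing them by interpretation gives a different response count. The most plausible reading, that uninformative cells do not count, removes the PD and no-change PR problems but leaves single-parameter patients with no PR route under the two-of-group-A rule.

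The fall in power from 0.90 to 0.85, 0.77 or 0.67 rests on assumed losses of 10%, 20% or 30%. It is an upper bound for each share, because it takes none of these patients to reach CR and applies the loss to all 26 patients, although T-LGL patients in the pooled ORR are assessed differently. Section 3.1.2 shows that single-site patients may enter, not how many will. The inflation figures in the other direction are equally conditional on an assumed share.

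**What to change.** Amend the footnotes to the table in 10.2, before Phase II responses are assigned:

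1. State that 'Any' and 'not done' cells never count as met criteria for PR or PD.
2. Name the response categories to which # applies, and extend it to constitutional symptoms.
3. State that a group A parameter counts toward PR only if it was abnormal at baseline.
4. Leave the group B cells as they are, so that an adequate count still qualifies. Applying the baseline-abnormal condition to group B would bar PR for any patient whose three counts are all adequate at entry.
5. Prespecify how a patient with only one abnormal group A parameter at baseline is classified for PR, reconciled with the cited IWCLL 2008 criteria.

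The cost is a protocol amendment to the footnotes and matching wording on the response form. No new data, visits or patients are needed.
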